7.16.10 Additional Blood Sample for Insulin Like Growth Factor Binding Protein 2 (IGFBP-2)

An additional blood sample (3.5 ml) for IGFBP-2 analysis will be collected at the screening or baseline visit, 3 month, and the 6 month visit. IGFBP is a useful biomarker of response, as over expression of IGFBP-2 has been associated with cancers and overgrowth syndromes. In a short treatment trial, we may be able to capture changes in IGFBP expression due to everolimus that shows promising evidence of therapeutic value in patients with PTEN. This measure will serve as a surrogate biomarker of effect. Samples will be de-identified and sent to the Genomic Medicine Institute Biorepository at Cleveland Clinic for analysis.

7.16.11 Microbiome/Mycobiome Sample Collection

When possible, we will collect optional saliva, urine, and fecal samples from all patients at baseline, month 3, and month 6 of the double-blind treatment phase and during the open label phase. Patients will receive the kits at home from Cleveland Clinic. Coordinators will instruct the participant/family to collect the samples ±14 days from the onsite visit. Once the samples are collected, the kit should be shipped back to Cleveland Clinic. The kit will also contain these instructions, all materials needed to collect the samples, and a return label.

These samples will be sent for storage at the Genomic Medicine Biorepository (GMB). If funding becomes available, future correlative studies will investigate PTEN pathway protein extraction and quantification, RNASeq, proteomic, microbiomic, and mycobiomic analyses.

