3.4.5 Everolimus Pharmacokinetics

The pharmacokinetic characteristics of everolimus have been extensively investigated in the context of the drug's development as an immunosuppressant in solid organ transplantation where everolimus was administered twice daily as a part of an immunosuppressant multi-drug regimen consistently including cyclosporin A and glucocorticoids. Recent Phase I studies provide steady-state pharmacokinetics for both the weekly and daily schedules at varying dose levels in patients with advanced cancers.

Everolimus is rapidly absorbed after oral administration, with a median time to peak blood levels (t_{max}) of 1-2 hours post dose. The extent of absorption is estimated to be above 11%. The area under the blood concentration-time curve (AUC) is dose-proportional over the dose range tested while maximum blood concentration C_{2h} appears to plateau at dose levels higher than 20 mg. The terminal half-life in cancer patients averaged 30 hours, which is similar to that in healthy subjects. Inter-patient variability is moderate with the coefficient of variation (CV) of approximately 50%. A high-fat meal altered the absorption of everolimus with 1.3-hour delay in t_{max} a 60% reduction in C_{2h} and a 16% reduction in AUC. In whole blood, approximately 80% of everolimus is contained in red blood cells. Of the fraction of drug contained in plasma, 74% is protein-bound. The apparent distribution volume (Vz/F) after a single dose was 4.7 L/kg. Everolimus is eliminated by metabolism, mainly by hydroxylation, then excreted into the feces >80%.

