4.3 Blinded Treatment Phase

All baseline procedures and evaluations should be completed within 6 weeks of the screening visit. If a patient's safety lab results are out of range, and the investigator has reason to believe there were situational factors affecting the values, the screening labs may be repeated. The safety evaluations may be completed at a lab that is geographically close to the participant and either provide the results of that analysis directly to the study team, or a sign a release so the study team can obtain the results from the lab. If a patient's baseline visit is more than 6 weeks after the screening visit the participant must have the safety labs re-drawn and processed, have the physical and neurological exam re-done, and the study team will confirm that there are no changes in the medical history or changes to the patient's current medications. If the screening safety evaluation and/or lab results are out-of-range, the participant will not be eligible to participate in the study. Patients who meet the study eligibility criteria following screening will be randomized to receive everolimus or placebo. The randomization ratio is 1:1, with one patient being randomly assigned to everolimus for every one patient randomly assigned to placebo. Treatment assignment via the RDCRN Members' Website should occur prior to the Baseline visit to allow adequate time for pharmacy preparation. Patients must start treatment within 7 days of the baseline visit, given that the participant still meets all inclusionary criteria and has not developed any exclusionary criteria. The medication should be taken at the same each day with a light, low-fat breakfast (i.e. 8:00 am with light breakfast).

The duration of blinded phase this study is 6 months. Patients will have their first daily dose of everolimus or placebo within 7 days of Visit 2 (baseline) and will continue on treatment for 6 months unless an intolerable toxicity occurs, withdrawal of consent, or investigator decision to discontinue the patient from study treatment.

Starting dose and adjustments are defined in Section. 6.2.

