4.4 Open Label Phase

Individuals in the placebo group will be invited to enter the 6-month open-label extension trial that will follow the same schedule as the blinded treatment phase. The final visit, or the Month 6 visit, in the blinded treatment phase will serve as the baseline visit of the open label phase if the participant chooses to enter the open label phase. Safety labs obtained at the end of the blinded phase will be used as baseline safety labs for the open-label phase. Similarly, the scores from the patient's developmental assessments will be used as both the 6-month blinded treatment phase data, and the baseline open-label phase data. Study staff should be prepared to dispense open label medication at this visit. If the patient is unable to enter the open-label phase at the final visit of the blinded treatment phase, the patient can come back within 2 weeks (+/- 2 weeks) of this visit date. Treatment, assessments, and outcomes of the open-label phase will also be identical to the double-blind phase.

The next visit will be the Month 1 visit. A PK sample, as well as specified safety labs, will be drawn on site and sent to LabConnect LLC. If the participant receives a dose adjustment at the time of this visit, study staff will work with the participant/family to get another sample taken at the study site or locally by a trained phlebotomist. The Month 3 visit and the Month 6 visit will include safety labs, developmental testing, optional EEG/AEP and eye tracking procedures, physical and neurological exams, vital signs, and other study questionnaires. A PK sample may also be collected from a patient experiencing an adverse event or side effect. The decision to obtain this sample will be made by the site physician.

The Month 2, Month 4, and Month 5 visits can be in person or by-phone if that is preferred by the family. If performed by phone, a phone interview will be performed to collect safety and other data, review AEs, and assess changes in mood or behavior. All applicable CRFs will be completed.

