7.5 Randomization Procedure

Subjects will be randomized 1:1 to everolimus or placebo after meeting all eligibility criteria. A designated member of the research team will communicate to the participant that randomization has occurred and sufficient study drug will be dispensed to cover the interval until the next study visit. This is a double-blind study. The study design allows patient unblinding during the double-blind phase only in very precise circumstances (section 7.6.1).

Randomization data are to be kept strictly confidential until the time of unblinding at discontinuation or at the time of final analysis. These data will not be accessible to anyone involved in the conduct of the study with the exception of the unblinded physicians, the Medical Monitor, the Data Safety and Monitoring Committee (DSMC), and the Data Management Coordinating Center (DMCC). The DSMC will review safety data as outlined in section 15. The identity of treatment arms will be concealed by the use of study drugs (everolimus and matching placebo) that are identical in packaging, labeling, schedule of administration and in appearance.

Prior to Baseline (Visit 2), the investigator or his/her designee will log onto the data system to verify that the patient fulfills all eligibility criteria and randomize the patient to a treatment arm. The system will assign a randomization arm, as described in the 7904 Manual of Procedures. The pharmacy will be responsible for dispensing the active drug or placebo based on the procedures outlined in the 7904 Pharmacy Manual of Procedures. The randomization will be stratified by age. Age will be stratified by two levels. Level 1 will be participants aged 5-21 years old, and level 2 will be 22-45 year olds. Permuted block sizes of two and four will be used. At the conclusion of the 6-month double-blind phase, the blind will be broken immediately. Individuals on the active drug will exit the study, and those who were on placebo will be invited to join the open label phase.

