7.7 Treating the Patient

7.7.1 Study Drug Administration

Everolimus or placebo will be dispensed by the study center personnel on an outpatient basis. Patients will be provided with study drug at Visit 2 (Baseline), and each subsequent on-site visit for self-administration at home.

The first dose of everolimus or placebo must be taken within 7 days of Visit 2 (Baseline). Patients will be instructed to take everolimus or placebo by mouth regularly, with the dose being taken at the same time in the morning every day. Everolimus or placebo tablets should be swallowed whole with a glass of water. The tablets should not be chewed or crushed. Any dietary habits around the time of everolimus or matching placebo intake should be as consistent as possible throughout the study. The extent of absorption of everolimus through topical exposure is not known. Therefore, patients/caregivers are advised to avoid contact with the everolimus or placebo tablets and should wear gloves and should wash their hands thoroughly before and after administration. If vomiting occurs, no attempt should be made to replace the vomited dose. Patients should be instructed that if they miss a dose one day, they must not take any extra dose the next day.

Patients should be requested to bring their unused study drug, including the empty blister packs, to the clinic at each visit.

Patients will receive treatment with study drug for 6 months or until the occurrence of unacceptable toxicity or the investigator or patient decides that continuation is not in the best interest of the patient. Interruption for toxicity should follow the instructions in Table 3.

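### The ±14-day window for home microbiome kits is not tied to dosing, so some everolimus-arm baseline kits can be on drug and post-visit Month 6 kits can lose the randomised exposure contrast

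*Combined protocol and SAP*

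**What the plan says.** Section 7.16.11 plans home kits for saliva, urine and feces "from all patients at baseline, month 3, and month 6 of the double-blind treatment phase and during the open label phase". The timing rule is the same throughout: "Coordinators will instruct the participant/family to collect the samples ±14 days from the onsite visit". The kits are optional and go into storage, and analysis depends on later funding. The purpose is given in section 2.3, an exploratory objective that asks whether everolimus alters the gut microbiome and mycobiome and whether any change tracks clinical improvement.

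Three other parts of the protocol fix where drug exposure begins and ends around those visits:

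- **Baseline.** Section 4.3: "Patients must start treatment within 7 days of the baseline visit". Section 7.7.1 says the same of the first dose.
- **Month 6, everolimus arm.** Section 7.5: "At the conclusion of the 6-month double-blind phase, the blind will be broken immediately". Sections 7.5 and 7.6 have everolimus patients leave the study at that point, and section 7.7.2 has unused drug returned at the last visit.
- **Month 6, placebo arm.** These patients are invited into the open-label phase. Section 4.4, on the Month 6 visit: "Study staff should be prepared to dispense open label medication at this visit". The same section also allows a later return to start open label.

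Tables 13A and 13B mark the kits by visit only. Neither they nor section 7.16.11 places a kit before the first dose, before the end of blinded treatment, or before the first open-label dose.

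**The concern.** A symmetric window around a visit is safe only if exposure is the same on both sides of the visit. That is true at Month 3, when both arms are in the middle of blinded treatment. It is not true at baseline, where drug starts at or shortly after the visit, or at Month 6, where blinded drug stops and some placebo patients start everolimus.

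A family can therefore follow the instruction exactly and still return a mistimed sample. An on-drug baseline in the everolimus arm hides part of the within-patient change. A post-visit Month 6 kit no longer compares patients on everolimus with patients on placebo. The effect depends on arm, so it acts as bias and not only as noise. It cannot be repaired afterwards, because a pre-drug sample cannot be collected once dosing has begun.

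**Working it through.** The plan gives no sample size, power or timing figure for these samples, so there is nothing of its own to reproduce. The check is date arithmetic, with blood kinetics added.

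**Inputs**
- Kit window: day −14 to day +14 around the visit, 28 days in total (7.16.11).
- First dose: day 0 to day 7 after the baseline visit (4.3, 7.7.1).
- Allocation 1:1 (7.5), with at most 40 randomised, or 20 per arm (sections 1 and 17.1).
- Month 6: blinded drug taken to stop at the visit (day 0). Open-label start is possible on day 0, or later through a return visit within two weeks ± two weeks, read here as day 0 to day 28 (4.4).
- Half-life: "The terminal half-life in cancer patients averaged 30 hours, which is similar to that in healthy subjects" (3.4.5).

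**Baseline kit, everolimus arm.** A kit used on day +14 follows the first dose by 14 − 7 = 7 to 14 − 0 = 14 days. From day +8 onward, every kit from a patient who kept the 7-day start rule is post-dose. On day +8 itself, exposure may be as short as 1 day.

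Assume collection dates are spread evenly over the window. The share of kits used after a first dose on day *d* is (14 − *d*)/28:
- *d* = 0: 14/28 = 50%
- *d* = 7: 7/28 = 25%

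This is the share within the everolimus arm. Placebo tablets do not affect a baseline, so with equal kit return in both arms the share of all baseline kits is half of that, 12.5% to 25%. If all 40 patients returned a kit, that is 5 to 10 of the 20 everolimus-arm kits.

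**Month 6 kit.** Under the same even-spread assumption, 14/28 = 50% of kits fall after the visit.
- Everolimus arm: such a kit is up to 14 days off drug.
- Placebo arm: on day +14 the patient has had 14 days of everolimus if open label began on day 0, falling to 0 days if the start is delayed or the invitation declined.

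**Blood exposure.** Assume first-order kinetics and steady daily dosing. The fraction left after stopping is 2^(−t/30 h), and the fraction of steady state after starting is 1 − 2^(−t/30 h).

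| Days | Remaining after stopping | Of steady state after starting |
|---|---|---|
| 1 | 57.4% | 42.6% |
| 2 | 33.0% | 67.0% |
| 7 | 2.1% | 97.9% |
| 14 | 0.04% | 99.96% |

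Fourteen days is 336/30 = 11.2 half-lives. With similar doses and a same-day stop and start, blood exposure in the former placebo patient overtakes that in the former everolimus patient after about 30 h. These figures describe drug in blood only.

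**With dose-tied windows.** Baseline exposure at collection becomes 0 days (now up to 14). At Month 6, time off drug in the everolimus arm and time on everolimus in the placebo arm both become 0 days (now up to 14 each).

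**The case against.** The strongest reply is that little hangs on this. The samples are optional and collected when possible, analysis awaits funding, and section 17 specifies no microbiome model. Month 3 kits still give a clean comparison of the randomised arms. Doses are recorded on case report forms (7.7.2) and samples are tracked on data collection sheets (16.4), so exposure at collection could be worked out wherever the collection date is captured. Site instructions may also be tighter than the protocol; the Manual of Procedures is not among these documents. All of this stands and keeps the point modest. It does not remove it: the protocol states a rule, and following that rule yields mistimed samples.

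A reader might also infer more than the documents support:

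- **That 25–50% of all baseline kits are contaminated.** That share applies to the everolimus arm only, and only if dates are evenly spread, for which the documents give no basis.
- **That placebo patients would enter open label with no clean reference.** Table 13B schedules no open-label baseline kit, but these patients' blinded baseline and Month 3 kits are also everolimus-free.
- **That exposure is always swapped at Month 6.** A full swap needs a late kit and a placebo patient who accepts open label and starts at the visit. Section 4.4 makes entry optional and allows a delay.
- **That swapped blood levels mean a reversed microbiome effect.** No section says how fast the microbiome or mycobiome responds to starting or stopping everolimus. At that visit one arm has had about six months of drug and the other at most 14 days.

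**Conclusion.** The point holds as a timing flaw in an exploratory sample collection and is worth correcting. As written, the window permits on-drug baseline kits in the everolimus arm. It also permits Month 6 kits that are off drug in the everolimus arm and either on everolimus or off drug in the placebo arm. Each case weakens the between-arm exposure contrast that section 2.3 needs.

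The baseline size given in the working is conditional on even spread and equal kit return; actual collection dates are unknown. The Month 6 reading assumes that everolimus patients stop at the visit and receive none elsewhere. Only kits used after the visit are at risk. Month 3 kits and placebo patients' blinded baseline kits are sound, and neither the primary safety endpoint nor the neurocognitive composite is affected.

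**What to change.** Amend section 7.16.11 and the kit instructions as follows:

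- Month 3: keep ±14 days.
- Baseline: collect within the 14 days before the first dose.
- Double-blind Month 6: collect within the 14 days up to the last blinded dose, and before any open-label dose.
- Record the collection date and the last-dose date on the kit form, and analyse any sample outside these limits by actual exposure.

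This changes one or two sentences and adds two date fields. Visits, dosing, kit numbers and sample types stay as they are. The cost is that the windows become one-sided: families need the kits in hand earlier, and a few late kits may be unusable for the planned contrast.

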7.17 Data from Samples

Data obtained from samples may also be shared with publically accessible databases, such as the database of Genotypes and Phenotypes (dbGaP).

7.18 Medical Records

We will collect medical records and clinical reports (if available) for screening and confirmation of medical history.

All medications (other than study drug) and significant non-drug therapies (including physical therapy and blood transfusions) administered after the patient starts everolimus and for up to 56 days (8 weeks) after study drug discontinuation must be listed on the CRF. All AEs and SAEs, regardless of causality will be collected and recorded up until 56 days (8 weeks) after study drug has been discontinued. This information will be collected on the CRFs listed under the phone call that happens after 1-month (28-days) of stopping study medication and/or completing the trial.

7.19 Follow-Up Questionnaires

All medications (other than study drug) and significant non-drug therapies (including physical therapy and blood transfusions) administered after the patient starts everolimus must be listed on the CRF. All AEs and SAEs, regardless of causality will be collected and recorded until the study drug has been discontinued. This information will be collected by phone call at 28 days post-treatment termination and for 8 additional weeks after, as indicated.

At the follow-up time point we will collect information about behavior (CBCL) and motor skills (DCDQ) as well as overall neurocognitive outcome. Parental questionnaires will be sent home and completed by the family of the participant. The questions about overall neurocognitive outcome will be conducted over the phone.

Table 13A: Double-Blind Treatment Phase Study Timeline

Measurement	Performed by	Rationale	Scree n (Visit 1)	Baseline ² (Visit 2)	Month 1 (Visit 3)	Month 2* (Visit 4)	Month 3 (Visit 5)	Month 4* (Visit 6)	Month 5* (Visit 7)	Month 6 (Visit 8)	Follow- up	PRN
Visit Windows				Within 42d of Screen	+/-14d	+/-14d	+/-14d	+/-14d	+/-14d	+/-14d	28d after last visit +/-14d	
Medical History	Clinician	Eligibility	Х	Х	X**	Х	X**	Х	Х	X**	Х	
Clinical Interview	Clinician	Eligibility + Safety	Х	Х	X**	Х	X**	Х	Х	X**		
Inclusion/ Exclusion criteria	Clinician	Eligibility	Х	X								
CGI Scale: Severity & Improvement	ΙĒ	Efficacy		X ³	X**	X ⁵	X**	X ⁵	X ⁵	X**		
Vital Signs	Clinician	Safety	Х	Х	Х		Х			Х		
Physical / Neurological Exam	Clinician	Safety	Х							X**		х
Dermoscopy	Clinician	Efficacy		Х			X**			X**		

Microbiome/ Mycobiome Sample Collection		Efficacy		x			х			х		
Tanner Staging	Clinician	Safety		Х						Х		
Side-effects (CTCAE v5.0 + DOTES)	Clinician	Safety	Х	х	X**	Х	X**	Х	Х	X**	Х	
Laboratory tests ¹	Lab	Safety	Х		Х		Х			Х		Х
Everolimus level (only done after M1 if needed)	Lab	Dose Adjust			х							х
PTEN-associated proteins	Lab	Efficacy	X ⁴	X ⁴			Х			x		
Concomitant treatment log	Clinician	Safety+ Efficacy	Х	Х	Х	Х	Х	Х	X	х	Х	
Autism Diagnostic Interview- Revised	Clinician	Sample Description		х								
Primary Efficacy Outcome Neurocognitive Composite	Clinician	Efficacy		х			x	5		Х	х	
Columbia- Suicide Severity Rating Scale	Clinician	Safety	Х		X**		X**			X**		
Conners' Continuous Performance Test (CPT-3/K- CPT-2)	Clinician	Efficacy	х	х	.0	O	х			х		
Stanford-Binet Fifth Edition (SB- 5) / Mullen Scales of Early Learning (MSEL)	Clinician	Efficacy	Х							x		
Stanford-Binet Working Memory Subscale Only	Clinician	Efficacy		x			х					
Purdue Pegboard (PP)	Clinician	Efficacy	Х	Х			Х			Х		
Wechsler Processing Speed Index Wide Range	Clinician		2	Х			х			х		
Assessment of Memory and Learning-2 (WRAML-2)	Clinician	Efficacy		х			X**			X**		
Peabody Picture Vocabulary Test – Fourth Edition (PPVT-4)	Clinician	Efficacy		Х			X**			X**		
Expressive Vocabulary Test – Second Edition (EVT-2)	Clinician	Efficacy		x			X**			X**		
Autism Diagnostic Observation Schedule (ADOS-2)	Clinician	Efficacy		х						х		
Social Responsiveness Scale – Second Edition (SRS-2)	Parent Report	Efficacy		х			х			х		

Repetitive Behavior Scale – Revised (RBS-R)	Parent Report	Efficacy	X	Х		Х		
Developmental Coordination Disorder Questionnaire (DCDQ)	Parent Report	Efficacy	x	x		x	x	
Behavior Rating Inventory of Executive Function (BRIEF)	Parent Report	Efficacy	x	Х		X		
Adult/Child Behavior Checklist	Parent Report	Efficacy	x	Х		X	X	
Sensory Profile Questionnaire - Short Form (SPQ)	Parent Report	Efficacy	X	x		х		
Vineland Adaptive Behavior Scales (VABS-III) – caregiver report	Parent Report	Efficacy	x	х		X		
Eye Tracking (Optional)	Clinician	Efficacy	×	х		Х		
Resting State EEG/Auditory Evoked Potentials (Optional)	Clinician	Efficacy	x	x		x		
Participant Unblinding						X**		Х

¹Coagulation testing will only be performed at screening, month 3 and month 6. Pregnancy testing, serum is done at screening and month 6 and urine may be used for onsite visits (if deemed clinically necessary) for women of childbearing potential.

2 Monthly visit windows are calculated based on date of Baseline visit.

CGI: Clinical Global Impressions Scale; IE: Independent Evaluator; CTCAE: Common Terminology Criteria for Adverse Events; DOTES: Dosage Record and Treatment Emergent Symptom Scale; **: primary outcome mesaure only.

Table 13B: Open Label Treatment Phase Study Timeline

	- P	or rioutino			11011110						
Measurement	Performed by	Rationale	Baseline ² (Visit 9)	Month 1 (Visit 10)	Month 2* (Visit 11)	Month 3 (Visit 12)	Month 4* (Visit 13)	Month 5* (Visit 14)	Month 6 (Visit 15)	Follow- up	PRN
Visit Windows			Within 2 weeks of Phase A, Month 6	+/-14d	+/-14d	+/-14d	+/-14d	+/-14d	+/-14d	28d after last visit +/-14d	
Medical History	Clinician	Eligibility	#	X**	X	X**	Х	Х	X**	Х	
Clinical Interview	Clinician	Eligibility + Safety	#	X**	Х	X**	Х	Х	X**		
Inclusion/ Exclusion criteria	Clinician	Eligibility	X								
CGI Scale: Severity & Improvement	IE	Efficacy	X ³ **	X**	X ⁴	X**	X ⁴	X ⁴	X**		
Vital Signs	Clinician	Safety		Χ		x			Х		
Physical / Neurological Exam	Clinician	Safety							X**		х

³At the baseline visit, only the CGI: Severity scale will be completed.

⁴PTEN-associated protein blood collections will be collected at either the screening or baseline visit (as well as at the 3 month and 6 month visits)

⁵CGI optional for phone interviews month 2, month 4, and month 5.

^{*=} May be performed by phone or in person

^{**=} May be performed by phone/videoconference under extenuating circumstances (note: Physical / Neurological Exam can not be completed in full remotely, but a modified version can be performed)

Dermoscopy	Clinician	Efficacy				X**			X**		
Microbiome/	Jiiiilolaii	Lindacy				^					
Mycobiome Sample Collection		Efficacy				х			x		
Tanner Staging	Clinician	Safety							Х		
Side-effects (CTCAE v5.0 + DOTES)	Clinician	Safety	#	X**	х	X**	х	х	X**	х	
Columbia-Suicide Severity Rating Scale	Clinician	Safety		X**		X**			X**		
Laboratory tests ¹	Lab	Safety	#	Х		Х			Х		Х
Everolimus level (only done after M1 if needed)	Lab	Dose Adjust		х							Х
PTEN-associated proteins	Lab	Efficacy				Х			X	,	
Concomitant treatment log	Clinician	Safety+ Efficacy	#	Х	Х	Х	х	Х	X	Х	
Primary Efficacy Outcome Neurocognitive Composite	Clinician	Efficacy	#			х	O		х	х	
Conners' Continuous Performance Test (CPT-3/K-CPT-2)	Clinician	Efficacy				x			x		
Stanford-Binet Fifth Edition (SB- 5) / Mullen Scales of Early Learning (MSEL)	Clinician	Efficacy							х		
Stanford-Binet Working Memory Subscale Only	Clinician	Efficacy				Х					
Purdue Pegboard (PP)	Clinician	Efficacy				Х			Х		
Wechsler Processing Speed Index	Clinician		30			Х			Х		
Wide Range Assessment of Memory and Learning-2 (WRAML-2)	Clinician	Efficacy				X**			X**		
Peabody Picture Vocabulary Test – Fourth Edition (PPVT-4)	Clinician	Efficacy				X**			X**		
Expressive Vocabulary Test – Second Edition (EVT-2)	Clinician	Efficacy				X**			X**		
Autism Diagnostic Observation Schedule (ADOS-2)	Clinician	Efficacy							х		
Social Responsiveness Scale – Second Edition (SRS-2)	Parent Report	Efficacy				Х			Х		
Repetitive Behavior Scale – Revised (RBS-R)	Parent Report	Efficacy				Х			Х		

Developmental Coordination Disorder Questionnaire (DCDQ)	Parent Report	Efficacy		Х		X	х	
Behavior Rating Inventory of Executive Function (BRIEF)	Parent Report	Efficacy		Х		X		
Adult/Child Behavior Checklist	Parent Report	Efficacy		X		X	X	
Sensory Profile Questionnaire - Short Form (SPQ)	Parent Report	Efficacy		Х		х		
Vineland Adaptive Behavior Scales (VABS-III) – caregiver report	Parent Report	Efficacy		X		X		
Eye Tracking (Optional)	Clinician	Efficacy		Х		X		
Resting State EEG/Auditory Evoked Potentials (Optional)	Clinician	Efficacy		Х	C.	х		

¹Coagulation testing will only be performed at screening, month 3 and month 6. Pregnancy testing, serum is done at screening and month 6 and urine may be used for onsite visits (if deemed clinically necessary) for women of childbearing potential.

CGI: Clinical Global Impressions Scale; IE: Independent Evaluator; CTCAE: Common Terminology Criteria for Adverse Events; DOTES: Dosage Record and Treatment Emergent Symptom Scale;**: primary outcome mesaure only.

Table 14: Blood Collection Amounts in mL

Visit Name	Screen (Visit 1)	Baseline ² ^‡ (Visit 2)	Month 1‡ (Visit 3)	Month 2*‡ (Visit 4)#	Month 3‡ (Visit 5)	Month 4*‡ (Visit 6)#	Month 5‡ (Visit 7)#	Month 6‡ (Visit 8)	PRN‡
Time point		Within 42d of Screen	+/-14d	+/-14d	+/-14d	+/-14d	+/-14d	+/-14d	
Serum/RNA/plasma storage (optional)	3.5×	3.5×			3.5			3.5	
IGFBP-2 (optional)	3.5×	3.5×			3.5			3.5	
Serology Panel: Hepatitis B and C, or HIV (as needed)	9.0								

²Monthly visit windows are calculated based on date of Baseline visit.

³At the baseline visit, only the CGI: Severity scale will be completed.

⁴CGI optional for phone interviews month 2, month 4, and month 5.

^{*=} May be performed by phone or in person

^{**=} May be performed by phone/videoconference under extenuating circumstances (note: Physical / Neurological Exam can not be completed in full remotely, but a modified version can be performed)#=procedures may be carried over from the Double-Blind Month 6 visit, if within 2 weeks of the visit.

Hormone Testing/ Serum Pregnancy (if needed)*	5.0					5.0	
Chemistry Panel **	5.0		4.0	4.0		5.0	
Hematology	3.0		3.0	3.0		3.0	
HbA1c	3.0						
Coagulation Studies PT/PTT/INR	4.5			4.5		4.5	
Everolimus level***			3.0				3.0
Total Blood Drawn (mL)	36.5	7.0	10	18.5		24.5	

^{*} For patients over the age of 7, hormone testing collected on all participants only at screening. For participants under the age of 7, estradiol, LH, and FSH will be tested. Serum Pregnancy collected at screening and Month 6 for female participants of childbearing potential.

